**Table 6 Imputation of lab values below/above the limit of quantification**

Lab Test	Characteristic value	Derived Numeric value	
Bilirubin	<2	2	
Direct Bilirubin	<2	2	
Estradiol	<61	61	
Luteinizing Hormone	<0.1	0.1	
Specific Gravity	>1.045	1.045	

## 6. SAMPLE SIZE AND POWER CONSIDERATIONS

## 7. STATISTICAL METHODOLOGY

### 7.1 Blinded Data Review

Prior to database lock, a blinded data review meeting (BDRM) will be conducted. Protocol deviations, protocol defined analysis populations will be confirmed during the meeting. Additional data handling rules may be introduced as results of data review. Should additional

data handling rules be confirmed during the meeting, they will be incorporated into the analyses planned in this SAP.

PK data that are considered "invalid" will be flagged in the listing. The PK data handling will be assessed during BDRM prior to database lock and in the investigation of PK data handling assessment after unblinding. A separate PK data handling document will be produced to cover both pre- and post- unblinding decisions. If PK sample handling errors or other factors identified after data unblinding and these errors have led to unexpected erroneous data, then these erroneous data will be regarded as "invalid".

## **7.2 Disposition of Subjects**

The number of subjects who enter screening will be summarized, and the percentage of these subjects who fail to meet entry criteria will be reported for total subjects.

Screen failures will be summarized in total and by each reason for screen failure.

The number of subjects who enter run in will be summarized. Run in failures will be summarized in total and by each reason for run in failure. (Table 14.1.1.2)

Subject disposition will be summarized for subjects completion status and discontinue reasons in tables for each treatment group, MT-8554 overall and total subjects.

The number and percentage of subjects in each analysis population will be summarized for each treatment group, MT-8554 overall and total subjects. (Table 14.1.1.1)

The data listing for Subject disposition will be generated.

## **7.3 Demographic and Other Baseline Characteristics**

The subject demographic and baseline characteristic will be summarized by treatment in table and presented in data listing for the safety population. (Table 14.1.2)

## **7.4 Medical History**

The subjects medical and surgical history will be summarized by treatment, SOC and PT in table and presented in data listing for the safety population. (Table 14.1.3)

The count and percentage of subjects who had at least one medical history or surgical history will be presented. For each medical history or surgical history term, the count and percentage of subjects will be presented.

In the table, SOC is sorted by International order; then within SOC, PT is sorted by descending counts under MT-8554 Total column, then descending counts under Placebo column, then alphabetic order for PTs with the same count.

## **7.5 Prior or Concomitant Medications**

The prior and concomitant medications will be summarized in table by treatment group and presented in data listing for the SAF population. (Table 14.1.4.1, Table 14.1.4.2) The data will be coded using World Health Organization Drug Dictionary (WHO Herbal Dictionary). The summaries will be by ATC level 2 and preferred name.

The count and percentage of subjects who had at least one prior or concomitant medication will be presented. For each prior or concomitant medication term, the count and percentage of subjects will be presented.

Prior medications are those which stopped prior to first dose of double-blind study medication. Concomitant medications are medications that started prior to, on or after date of first dose of double-blind study medication and ended on or after date of first dose of double-blind study medication. This includes medications deemed as ongoing at the end of study.

## **7.6 Study Medication Exposure**

Duration of exposure to double-blind study medication in days will be summarized in table and presented in data listing for the safety population. (Table 14.1.5)

## **7.7 Treatment Compliance**

Compliance to Double-Blind study medication will be presented for the ITT population in table by treatment. (Table 14.1.6)

All study medication administration and accountability data will be listed by subject.

## **7.8 Protocol Deviations**

The major protocol deviations will be presented in data listings.

[figure not shown]
## **7.9 Efficacy Assessments**

All Efficacy Tests data will be listed.

### 7.9.1 Primary Efficacy Analysis

Unless otherwise noted, these analyses are performed using ITT population.

In order to deal with multi-endpoints multiplicity, the primary efficacy analyses of primary and secondary endpoints will be judged to statistical significance in the order shown below.

#### 7.9.1.1 Efficacy Analysis for Co-Primary Efficacy Endpoints

Change from baseline to Week 4 and Week 12 in the average daily frequency of moderate to severe VMS will be analyzed using repeated measures ANCOVA model with an unstructured covariance structure. The analysis model will include baseline value of the endpoint as a covariate and visits, treatment, interaction between visit and treatment, interaction between baseline and visit, antidepressant using (Y,N) , and interaction between antidepressant using (Y,N) and treatment as fixed effect. Baseline, weeks 1, 2, 3, 4, ..., 12 will be used for this analysis. (Table 14.2.1.1.A)

Similar analyses will be conducted for VMS severity score. (Table 14.2.1.2.A). The primary efficacy analysis will also be performed using PP population. (Table 14.2.1.1.B, Table 14.2.1.2.B)

If the normality assumption for the model is not met, the non-parametric method ranked ANOVA will be performed.

The scatter Plot of Mean change from baseline in VMS frequency and severity by treatment will be generated. (Figure 14.2.3.1, Figure 14.2.3.2). The scatter Plot of observed mean values of VMS frequency and severity by treatment will be generated. (Figure 14.2.4.1, Figure 14.2.4.2). The bar graph of Mean change from baseline in VMS frequency and severity at Weeks 4 and 12 by treatment will be generated. (Figure 14.2.5.1, Figure 14.2.5.2) The box plot of change from baseline in VMS frequency and severity by treatment will be generated as well. (Figure 14.2.6.1, Figure 14.2.6.2)

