10.3.6 Analysis of secondary endpoints

After the main analyses for all co-primary endpoints successfully show the treatment effect, efficacy analyses for the secondary endpoints may be continued in a fixed order as deemed appropriate as follows.

1. The proportion of responders at Weeks 4 and 12 (i.e., subjects with cutoff number* or greater reduction in the average daily frequency of moderate and severe VMS compared to baseline).
2. Time to response, defined as time (in weeks) from randomization to the first time subjects meet responder criteria (i.e., cutoff number* or greater reduction from baseline in the average daily frequency of moderate and severe VMS).
3. Change from baseline to Weeks 4 and 12 in the ISI total score.

*Note: The cutoff number of responder criteria will be calculated using anchor-based method, using PGIC as the anchor. The satisfied subjects will be defined as those whose PGIC response is either 6 or 7. The cutoff number is defined as numerical value to maximize the sum of sensitivity and specificity for change from baseline in average daily frequency of moderate to severe VMS. This calculation will use weeks 4, 12 and 4 arms pooled data.

The proportion of responders will be analyzed using a logistic regression model with treatment as fixed effect and baseline as covariate.

The time to response will be analyzed with a log-rank test for each MT-8554 arm with placebo, with treatment as fixed effect and baseline as covariate. The VMS severity score and ISI will be analyzed using a procedure similar to the main analyses for co-primary endpoints.

Further details will be provided in the SAP.

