10.3.8 Subgroup analysis

The primary analysis model with applicable covariates will be conducted for ITT subjects who used antidepressants during the study. More subgroup analyses may be defined in the SAP.

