## 7.9.2 Secondary or other exploratory Efficacy analysis

### 7.9.2.1 Efficacy Analysis for paired comparison as Secondary analysis

For all the efficacy endpoint that treatment effect is significant in the Section 7.9.1.1 Primary Efficacy Analysis, the paired comparison of the placebo vs each active dose will be performed using the same model.

Point estimates and 95% CIs for the difference between each active dose and placebo will be generated as well.

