#### 7.9.4 Sensitivity Analysis of Efficacy Endpoints

Sensitivity analyses for Efficacy Endpoints as following.

The sensitivity analysis will be conducted using primary analysis model with applicable covariates for ITT subjects without using antidepressants. (Table 14.2.2.1.A, Table 14.2.2.1.B, Table 14.2.2.2.A, Table 14.2.2.2.B)

The primary endpoints will also be analyzed using an ANCOVA model at week 4 and 12. The analysis model will include baseline value of the endpoint as a covariate and treatment as fixed effect. (Table 14.2.3.1, Table 14.2.3.2)

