## 7.12 Statistical/Analytical issues

### 7.12.1 Adjustments of covariates

In the efficacy analysis, repeated measures ANCOVA model with an unstructured covariance structure or ANCOVA will be performed with baseline as a covariate in order to consider the impact of the baseline on the change in each variable. More details were described in each analysis.

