**8. CHANGES FROM THE PROTOCOL**

Subgroup analysis of antidepressant using (Y, N) will not be performed because there are not enough subjects with using antidepressant for the analysis.

Analysis for PP Population does not apply to secondary endpoints. These analyzes were considered to be excessive.

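### The primary models keep a treatment-by-antidepressant interaction although the SAP says users are too few for a subgroup analysis; with no weighting stated, default equal weights would weaken the gating test if users are scarce.

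*SAP*

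**What the plan says.** SAP 7.9.1.1, following Protocol 10.3.5, analyses change in VMS frequency with a repeated measures model. Its fixed effects include antidepressant use and the "interaction between antidepressant using (Y,N) and treatment as fixed effect". Similar analyses are planned for the severity score, so the term carries over to both co-primary endpoints. In the SAP this interaction is not crossed with visit.

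Protocol 10.3.8 planned a subgroup analysis in users: "The primary analysis model with applicable covariates will be conducted for ITT subjects who used antidepressants during the study". SAP Section 8 withdraws it: "Subgroup analysis of antidepressant using (Y, N) will not be performed because there are not enough subjects with using antidepressant for the analysis". Section 8 gives no count and does not alter the primary models.

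These models act as a gate. SAP 7.9.1 states that "the primary efficacy analyses of primary and secondary endpoints will be judged to statistical significance in the order shown below", and the co-primary models come first in that order. SAP 7.9.2.1 limits the paired dose-placebo comparisons: "For all the efficacy endpoint that treatment effect is significant in the Section 7.9.1.1 Primary Efficacy Analysis". Protocol 10.3.6 takes up the secondary endpoints only "After the main analyses for all co-primary endpoints successfully show the treatment effect".

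On covariates, SAP 7.12.1 says the efficacy models "will be performed with baseline as a covariate in order to consider the impact of the baseline on the change in each variable" and refers to the individual analyses for further detail. None of the visible sections states LS-mean weights, the type of test for the treatment effect, or what happens if an arm has no users.

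**The concern.** A split judged too sparse to analyse on its own still shapes the confirmatory test. Once treatment interacts with antidepressant use, there is no single treatment effect. There is one in users and one in non-users, and the overall effect depends on how the two are weighted. The usual Type III test and default LS means give each half the weight, whatever the group sizes. A handful of users would then supply half of every dose-placebo estimate, and their sampling error would dominate its standard error. The estimate would also refer to a hypothetical population in which half the women take antidepressants.

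If an arm has no users, its equal-weight LS mean cannot be estimated at all. Protocol 7.5 describes 1:1:1:1 allocation and mentions no stratification by antidepressant use, so nothing visible guarantees users in every arm.

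At stake is a false negative at the first step of the testing order in a Phase II dose-selection study. A real effect could fail the gate and formally block the paired comparisons and the secondary endpoints.

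**Working it through.** **Inputs from the documents.** 91 subjects per arm (Protocol 4.1), four arms, 12 weekly visits (SAP 7.9.1.1), two-sided 5% (SAP 5.2), interaction not crossed with visit (SAP 7.9.1.1).

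**Assumptions.** The sample-size basis is not visible, so the plan's own power cannot be reproduced and 90% is assumed as a starting point. Also assumed: 2, 5, 9, 14 or 18 users in every arm, complete data, no true interaction, and compound symmetry with within-subject correlation rho = 0.7 (varied from 0.5 to 0.9).

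**Standard error ratio.** Compare the interaction model with equal weights against the main-effects model. Let n1 be the users per arm, p = n1/91 and k = (0.5 − p)²/[p(1 − p)].

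- 12-week average: ratio = √(1 + k)
- Single visit: ratio = √(1 + k(1 + 11·rho)/12). The inflation is smaller because all 12 visits inform the one interaction term.

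Example with 5 users: p = 0.0549 and k = 3.815. The 12-week-average ratio is √4.815 = 2.194. The Week 12 ratio is √(1 + 3.815 × 0.725) = 1.940. An exact generalised least squares calculation with 4 arms and 12 visits gives the same ratios. With observed-margin weights the ratio is 1.000 throughout.

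**Power.**

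- Gate test: a 3-df treatment test on the 12-week average. Power = P(noncentral χ²₃(ncp/ratio²) > 7.815), with ncp set to give 90% before inflation.
- Week 12 dose-placebo contrast: power = Φ(3.2415/ratio − 1.96), also 90% before inflation.

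| Users per arm | 12-week SE ratio | 3-df gate power | Week 12 SE ratio | Week 12 power | Week 12 power, rho 0.5 to 0.9 |
|---|---|---|---|---|---|
| 2 | 3.410 | 13.2% | 2.951 | 19% | 24–17% |
| 5 | 2.194 | 27.0% | 1.940 | 39% | 46–34% |
| 9 | 1.675 | 44.5% | 1.519 | 57% | 63–51% |
| 14 | 1.386 | 61.5% | 1.291 | 71% | 75–67% |
| 18 | 1.255 | 71.1% | 1.190 | 78% | 81–75% |

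**A common starting point.** The two power columns each start at 90% separately. If instead the effect is constant over weeks and 90% applies only to the Week 12 contrast, the 12-week average starts stronger: 3.2415/√0.725 = 3.807. On that basis, for 2, 5, 9, 14 and 18 users per arm:

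- The 1-df 12-week-average contrast starts at about 97% and falls to 20%, 41%, 62%, 78% and 86%.
- The 3-df test, if all doses share the effect, starts at 98% and falls to 18%, 40%, 64%, 82% and 89%.
- The 3-df test, if the effect rises in equal steps to the top dose, starts at 94% and falls to 14%, 30%, 50%, 68% and 77%.

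**Simulation check.** This used 2,000 runs per setting, 4 × 91 subjects, one summary value per subject and a standardized effect of 0.455 in all doses. Runs with an empty arm were left out. For user shares of 3%, 5%, 10% and 20%, the equal-weight 3-df test had 17%, 22%, 43% and 68% power. Observed margins gave 88% to 91% and the main-effects model 89% to 91%. With no true effect, the equal-weight test rejected in 4% to 6% of runs.

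**Chance of an arm without users.** 1 − [1 − (1 − prevalence)⁹¹]⁴ gives about 50% at 2% prevalence, 23% at 3%, 4% at 5% and 0.03% at 10%.

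**What Section 8 implies about the count.** The dropped analysis was the primary model run in users only. An unstructured covariance over 12 visits has 12 × 13/2 = 78 parameters, so even 18 users per arm might be called not enough. Section 8 therefore does not show which row of the table applies.

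**The case against.** The strongest objection is that the SAP nowhere adopts equal weights or Type III tests. What the text establishes is that the weighting is unstated, and one sentence could settle that. Dropping a users-only analysis while keeping a protocol-specified model term is also not a contradiction. All of this is true, and it is why the loss is stated as conditional. But the written model fitted with usual defaults gives the weaker test, and choosing the weights after unblinding would be a data-dependent decision on the gating analysis.

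Second, the user count is unknown. Stable-dose antidepressants are permitted, and the lowest rows of the table have no direct support. At 27 users per arm the 3-df test would still have about 83% power and the Week 12 contrast about 86%. This stands: the figures are illustrative, and the loss is modest at 18 per arm and above. The form of the gate test is also assumed, and a week-specific test loses less, as the table shows.

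Third, a failed gate need not hide the signal. SAP 7.9.4 has a non-user analysis and a plain alternative: "The primary endpoints will also be analyzed using an ANCOVA model at week 4 and 12". SAP 7.9.2.2 adds dose-response contrasts for frequency that are not stated to depend on the gate. Protocol 10.3.5 plans dose-placebo estimates without that condition. These soften the consequence, but none of them opens the formal gate.

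Finally, the public SAP lacks its output lists, so the gap can be asserted only for the visible text.

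**Conclusion.** The concern holds and should be fixed. The primary models keep an interaction with a factor that the SAP itself considers too thinly represented for a subgroup analysis, and the visible text sets neither the weighting nor a rule for an empty arm. With equal weights, 91 per arm and 90% starting power, the 12-week-average 3-df test keeps about 13% power at 2 users per arm and 71% at 18. The Week 12 contrast keeps 19% to 78% at rho 0.7. These figures rest on the assumed weighting, user counts, starting power and compound symmetry. The direction does not depend on the user count, except that the loss vanishes as the user share approaches one half. The harm is lost power, a shifted target population and possible non-estimability, not inflated type I error. Confidence in the size is medium because the user count is not visible.

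**What to change.** Before unblinding, keep antidepressant use as a main effect in the primary frequency and severity models, move the interaction to a supportive model, and declare the departure from Protocol 10.3.5 in SAP Section 8.

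If the interaction has to stay, pre-specify observed-margin weights for the overall treatment test and for every dose-placebo contrast, with a fallback to the main-effects model if any arm has no users.

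The first option costs a declared change, a small edit to the model code and one supportive table. The second costs a short weighting statement and the empty-arm rule. Neither needs new data or patients, and the sensitivity analyses in SAP 7.9.4 can stay as they are.

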10.3.5 Analysis of primary endpoints

Main Analysis

Change from baseline to Week 4 and Week 12 in the average daily frequency of moderate to severe VMS will be analyzed using a repeated measures analysis of covariance (ANCOVA) model with an unstructured covariance structure. The analysis model will include baseline value of the endpoint as a covariate; weeks, treatment, antidepressant using (Y,N), and interaction between antidepressant using (Y,N) and treatment as fixed effect. Relevant covariates will also be included in the model. If the normality assumption for the model is not met, a non-parametric method such as a ranked analysis of variance (ANOVA) will be performed.

The sensitivity analysis will be conducted using primary analysis model with applicable covariates for ITT subjects without using antidepressants.

Similar analyses will be conducted for VMS severity.

Comparison between each dose of MT-8554 and placebo will also be conducted using a repeated measures ANCOVA model. Point estimates and 95% CIs for the difference between each active dose and placebo will be obtained.

Further details will be provided in the SAP.

Secondary Analysis

The primary endpoints will also be analyzed using Maximum Contrast Methods with baseline value of the endpoint as a covariate, or slope approach¹³, as an analysis of the dose-response relationship. The detail will be specified in the SAP.

The primary endpoints will also be analyzed using an ANCOVA model.

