### **3.3 Final Analysis**

The final analysis will be conducted with unblinded data after database lock.

All the planned efficacy and safety analyses in this SAP will be performed by [REDACTED]

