#### **5.4.2 Definition of the average daily severity score of mild to severe VMS**

The daily VMS severity score is defined as  $(2xFmo + 3xFse)/(Fmo + Fse)$  for any day before the first dose day, and  $(1xFmi + 2xFmo + 3xFse)/(Fmi + Fmo + Fse)$  for any day on or after the first dose day, where Fmi, Fmo, and Fse are the daily frequencies of mild, moderate, and severe VMS, respectively. It will be rounded off the third decimal place and reported the value to the second decimal place.

The average daily VMS severity of mild to severe VMS at a time point (Baseline, Week 1, 2, 3, 4, ..., 12) is the average of the daily severity of available diary days in the corresponding 7-day window defined in Table 4.

A daily severity score of zero (0) is assigned if it is reported that no VMS occurred on that day. VMS data on the day of Week 12 visit is not used for the calculation of average daily VMS severity. If the count of available VMS data in a specific week is less than four (4), latest diaries in the previous window can be carried as needed to make 4 diaries available in this window. Then the average daily VMS severity in the week is calculated.

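### SAP 7.9.1.1 adds a ranked ANOVA to the co-primary analysis if normality fails, without saying how or when that is judged, whether it replaces the repeated measures ANCOVA, or whether it keeps baseline

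*SAP*

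**What the plan says.** SAP 7.9.1.1 gives the main model with its terms (baseline, visit, treatment, visit by treatment, baseline by visit, antidepressant use, antidepressant use by treatment), an unstructured covariance, and data from Weeks 1 to 12. The severity score is to be handled similarly. One sentence follows: "If the normality assumption for the model is not met, the non-parametric method ranked ANOVA will be performed".

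Protocol 10.3.5, and the synopsis in the same terms, is looser: "If the normality assumption for the model is not met, a non-parametric method such as a ranked analysis of variance (ANOVA) will be performed". It leaves details to the SAP. The SAP settles on a ranked ANOVA but adds no detail.

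Three other places bear on the point:

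- **Gates.** SAP 7.9.2.1 begins "For all the efficacy endpoint that treatment effect is significant in the Section 7.9.1.1 Primary Efficacy Analysis, the paired comparison", and runs those dose comparisons with the same model. Protocol 10.3.6 says "After the main analyses for all co-primary endpoints successfully show the treatment effect, efficacy analyses for the secondary endpoints may be continued".
- **Timing.** SAP 3.3: "The final analysis will be conducted with unblinded data after database lock". On the blinded review, SAP 7.1 says: "Protocol deviations, protocol defined analysis populations will be confirmed during the meeting". That section allows extra data handling rules but does not mention a normality check.
- **Original-scale results.** Protocol 10.3.5 also states: "Comparison between each dose of MT-8554 and placebo will also be conducted using a repeated measures ANCOVA model". SAP 7.9.4 adds an ANCOVA at Weeks 4 and 12.

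**The concern.** The sentence sits in the primary analysis section, not among the sensitivity analyses in SAP 7.9.4. That suggests replacement of the main model without stating it. Left open are the test or graphical rule, its level, which residuals and weeks it uses, whether frequency and severity are judged separately, when it is done, and which model terms survive ranking.

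Two analysts following the text could therefore run different co-primary tests and disagree on significance. That result opens the dose comparisons and the secondary endpoints. If the choice comes after results by arm are known, the nominal 5% is no longer assured.

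The trigger is also likely to be met for severity. The weekly score is bounded, and SAP 5.4.2 states: "A daily severity score of zero (0) is assigned if it is reported that no VMS occurred on that day".

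**Working it through.** **1. Is the gap filled elsewhere?** SAP 7.1 (blinded review), 7.9.4 (sensitivity analyses), 7.12.1 (covariates), 7.12.4 (multiplicity) and 8 (changes from the protocol) do not settle it. SAP 7.12.1 puts baseline into the ANCOVA models but does not mention the ranked ANOVA. The SAP's list of tables is not in the text available and could not be checked.

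**2. Inputs from the documents.** Two-sided 5% (SAP 5.2); four arms, 1:1:1:1 (Protocol 7.5); 91 per arm (Protocol 4.1), and 4 × 91 = 364 agrees with the stated total. Effect size, SD and planned power are not visible in the public text.

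**3. Assumptions, not from the documents.** One time point, no dropout, 3-df treatment F test. Change = ρ × baseline + √(1 − ρ²) × gamma error of the given skewness, total SD 1. For power, the effect is linear across arms with largest difference 0.419 SD. The noncentrality is 91 × 0.419² × 5/9 = 8.88, which gives 70% power for the unadjusted F test on 3 and 360 df. There were 10,000 runs per setting.

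**4. Type I error per endpoint and week** (skewness 0.3 to 2, ρ from 0 to −0.7):

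| Rule | Type I error |
|---|---|
| ANCOVA alone | 4.7-5.5% |
| Shapiro-Wilk at 5%, followed mechanically | 4.6-5.6% |
| Better of ANCOVA and rank ANCOVA | 5.9-7.2% |
| Better of ANCOVA and ranked ANOVA without baseline | 5.9-9.1% |

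A second simulation with normal, t and gamma errors gave 5.0-5.6% for the mechanical rule and 7.1-8.2% for the better of ANCOVA and ranked ANOVA. For a severity-like score in which 5-30% of subjects have zero-VMS days, ANCOVA alone held 4.7-5.2% and the better-of-two rules gave 6.7-8.4%.

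**5. How often the trigger is met.** At 364 subjects, Shapiro-Wilk at 5% rejects in about 26%, 52% and 93% of trials at skewness 0.2, 0.3 and 0.5, and in every run of the severity-like score. The unstated level matters: at skewness about 0.32, levels of 0.01, 0.05 and 0.10 reject in about 35%, 57% and 68% of trials.

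**6. Power:**

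| Skewness | ρ | ANCOVA | Ranked ANOVA, no baseline | Rank ANCOVA |
|---|---|---|---|---|
| 0.5 | 0 | 0.703 | 0.704 | 0.703 |
| 0.5 | −0.5 | 0.829 | 0.695 | 0.816 |
| 1 | 0 | 0.709 | 0.776 | 0.775 |
| 1 | −0.5 | 0.825 | 0.720 | 0.851 |
| 2 | 0 | 0.707 | 0.976 | 0.975 |
| 2 | −0.5 | 0.824 | 0.824 | 0.946 |
| 2 | −0.7 | 0.945 | 0.747 | 0.976 |

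A separate run of the skewness 0.5, ρ = −0.5 case gave 0.82, 0.68 and 0.81. Following the 5% check mechanically to a ranked ANOVA without baseline gives 0.71 there. Rank ANCOVA matches or beats ranked ANOVA, to within simulation error, in every row.

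**7. Link to the planned model.** With complete data and visit crossed with treatment and baseline, the Week 12 difference from the 12-week model equals the one-week ANCOVA (0.0835 in both, one simulated data set). Adding the antidepressant terms changed it to 0.068. Those terms and dropout are not in the simulation.

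**The case against.** Several counter-arguments carry weight.

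- **Replacement is not stated.** The ANCOVA and its tables are specified unconditionally, and the later sentence can be read as adding a test. On that reading the ANCOVA result stands. A reader might infer that the co-primary decision is certain to move to ranks, or that original-scale estimates are lost. The documents support neither, given the dose comparisons in Protocol 10.3.5 and the ANCOVA in SAP 7.9.4.
- **An unblinded choice is not stated.** Residuals from a model with treatment need group membership, but masked labels would do, and pooled residuals need none. The documents fail to exclude a choice after unblinding. They do not plan one.
- **The 6-9% is not the error of the plan's rule.** It arises only if someone takes the better result, and its upper end needs the reading without baseline. With baseline kept, the maximum is 7.2%.
- **Dropping baseline is one reading.** The SAP writes ANOVA for PGIC, which has no baseline value, so that usage is weak evidence.
- **Joint success is harder.** Under a global null with the better test accepted throughout (skewness 1, correlation −0.5, assumed error correlations 0.4-0.7), both endpoints passed at both weeks in 0.6% of 2,000 runs, and at Week 12 alone in 1.8%. The per-endpoint rate still matters when only one endpoint is null.
- **The consequence is limited.** This is a Phase II dose-selection study, and SAP 7.12.4 treats secondary analyses of the primary variable as exploratory.
- **Ranks can be the better test.** At skewness 2 and ρ = 0, ranked ANOVA has 0.98 power against 0.71 for ANCOVA.

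These points limit the size of the problem and shape the remedy. None supplies the missing rule.

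**Conclusion.** The concern holds in a limited form. The co-primary analysis has a conditional branch whose trigger, timing, role and model terms are undefined, and the documents do not prevent the branch from being chosen after unblinding. That omission needs no assumption to establish.

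Its size is illustrative. If the more favourable test is chosen, type I error per endpoint and week goes from 5% to about 6-9%; under a fixed rule it stays near 5%. Read literally as a ranked ANOVA without baseline, the fallback cuts power from 0.82-0.83 to 0.68-0.70 at skewness 0.5 and correlation −0.5. Under strong skew the ordering can reverse. These figures rest on assumed skewness, correlation and effect, one time point, and no dropout.

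It would go too far to conclude that the plan inflates type I error as written, or that rank tests are unsuitable here. The fault is the open choice, together with a fallback that may omit baseline. The sponsor should correct it.

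**What to change.** - **SAP 7.9.1.1:** delete the conditional sentence. Before unblinding, name one primary analysis for each co-primary endpoint, by default the repeated measures ANCOVA, to stand whatever the residuals show.
- **SAP 7.9.4:** add a prespecified rank ANCOVA with baseline as covariate, not a ranked ANOVA, at Weeks 4 and 12 for both endpoints. State whether the antidepressant terms are included.
- **SAP section 8:** record the change from Protocol 10.3.5 and the synopsis.

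The direct cost is wording, one entry in section 8 and one table per endpoint. The statistical cost is power under strong skew. It is small at skewness 1 (0.71 for ANCOVA against 0.78 for ranks at correlation 0; 0.83 against 0.85 for rank ANCOVA at −0.5) and large at skewness 2 (0.71 against 0.98; 0.82 against 0.95). If blinded pooled data show strong skew in severity, the sponsor may name rank ANCOVA as the single primary test for that endpoint, provided that this is fixed before unblinding.

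A smaller change would keep the fallback and write down its test, level, residuals, weeks, model terms and a blinded decision before database lock. That would control type I error, but the power loss remains unless the ranked model keeps baseline.
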